4.2.5.2 Supplementary analysis

Inhomogeneity of treatment effect

A supplementary analysis that includes a treatment-by-visit interaction term in the model specified above will also be performed. The aim of this supplementary analysis would be to explore potential differences in treatment effect between visits, and thus the results of this analysis will be presented in the form of treatment effect estimate, with the corresponding 95% CIs, at each visit separately, and the p-value originating from a test of the treatment-by-visit interaction term.

Again, due to the early close-down of the study and the ensuing unavailability of late bicarbonate measurements, only measurements taken up to and including visit 17 (week 69) will be included in the mixed-effects model.

Probability as population summary measure

For each visit and treatment arm, the probability of bicarbonate > 22 mmol/L will be estimated with a simple percentage. For each visit, the difference in probability of bicarbonate > 22 mmol/L will also be estimated, together with a 95 % CI.

Again, due to the early close-down of the study and the ensuing unavailability of late bicarbonate measurements, only measurements taken up to and including visit 17 (week 69) will be included in the mixed-effects model.

4.2.6 Analysis of Secondary objective #5

Secondary objective #5: To determine if treatment with SZC, as adjunct to ACEi/ARB therapy (lisinopril or valsartan), is superior to placebo on maintenance of normokalaemia.

4.2.6.1 Main analysis

The secondary objective of evaluating the maintenance of normokalaemia will be evaluated by means of a GEE model that uses a logit link function and unstructured working correlation structure. This model will have the dichotomous classification in normokalaemic (S-K, as evaluated by c-lab, between 3.5 and 5 mmol/L) and non-normokalaemic (S-K < 3.5 or S-K > 5 mmol/L) at each visit as response. Similarly to the analysis of Secondary objective #4, the model will have visit and baseline potassium as covariates, as well as the ones specified earlier. The null hypothesis of no difference between the treatment arms will be tested by considering the estimate of the odds ratio for the treatment effect in this model. As for other analyses, the estimates of the treatment effect (i.e., odds ratios) alongside the corresponding 95% CI and p-values, will also be provided.

Again, due to the early close-down of the study and the ensuing unavailability of late potassium measurements, only measurements taken up to and including visit 17 (week 69) will be included in the GEE model; however, all available data, including the (quite few) late potassium measurements beyond visit 17 (week 69), will be summarised descriptively and listed.

4.2.6.2 Supplementary Analyses

Inhomogeneity of treatment effect

A supplementary analysis similar to that described in Section 4.2.5.2 for Secondary objective #4 will be performed. That is, a model that includes a treatment-by-visit interaction

term in the model specified above will also be constructed, and the treatment effect estimates for each visit, the corresponding CIs and the p-value for the test of significance of the interaction term, will be provided.

Again, due to the early close-down of the study and the ensuing unavailability of late bicarbonate measurements, only measurements taken up to and including visit 17 (week 69) will be included in the mixed-effects model.

Probability as population summary measure

Similarly, to analyses of Secondary objective #4, a supportive analysis that examines the difference in probability of normokalaemia between treatment arms will be performed.

4.3 Pharmacodynamic Endpoint(s)

Not applicable.

4.4 Pharmacokinetics

Not applicable.

4.5 Safety Analyses

The domain safety covers exposure, adverse events, clinical laboratory, vital signs, and ECG.

Tables will be provided for the safety sets, listings are provided for all enrolled subjects, or the safety sets, depending on the availability of data. For the tabular summaries, subjects that erroneously received incorrect IP during the maintenance phase of the study (SZC or Placebo) will be analysed as belonging to the treatment group they were randomized to.

As a rule, safety analysis will be presented for both On Treatment and During Study. Further, as a rule, the safety analyses will be presented separately for different phases, with events occurring during follow-up assigned to the study phase directly preceding the follow-up period.

4.5.1 Adverse Events

4.5.1.1 Definitions and Derivations

Oedema-related events are defined as AEs with the following PT terms: Fluid retention, Generalised oedema, Hypervolemia, Localised oedema, Oedema, Oedema Peripheral, Peripheral swelling.

Hypokalaemia is collected as an adverse event in the appropriate eCRF form. In particular, investigators are advised to report it as an AE if it leads to temporary or permanent discontinuation of SZC or SZC/placebo.

Hyperkalaemia is collected as an adverse event in the appropriate eCRF form.

Note that both hypokalaemia and hyperkalaemia could also be determined based on the central lab potassium evaluation, and would then be reported separately, see Section 4.5.2.

Severe hyperkalaemia requiring rescue is collected as an adverse event and is indicated directly by the investigator in the appropriate eCRF form.

Duration variables to be presented, where applicable (e.g., key subject information tables), are defined as follows:

- Time from planned treatment start date (in the respective treatment period) to onset of AE (days)
- Time from planned treatment start date (in the respective treatment period) to death (days)
- Time from planned treatment start date (in the respective treatment period) to AE becoming serious (days)
- Time from planned treatment start date (in the respective treatment period) to discontinuation of IP (days)
- Time from actual last dose date to death (days)
- Time from actual last dose date to AE start date (days)

The derivations for these variables will be the difference between the two dates stated above + 1 day.

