**Table 3 Risk Assessment of SZC and the Use of SZC with Lisinopril or Valsartan as Background Interventions**

Potential risk of clinical significance	Summary of data/rationale for risk	Mitigation strategy
Hypokalaemia (S-K < 3.5 mmol/L)	Common for SZC ( $\geq 1/100$ to $< 1/10$ ). In clinical trials, 4.1% of participants treated with SZC developed hypokalaemia.	Periodic monitoring of S-K and dose adjustment as necessary.
Oedema-related events (includes fluid overload, fluid retention, generalised oedema, hypervolaemia, localised oedema, oedema, oedema peripheral, peripheral swelling)	Common for SZC ( $\geq 1/100$ to $< 1/10$ ). In clinical trials with SZC, the most commonly reported adverse reaction was oedema-related events which were reported by 5.7% of participants treated with SZC; 1.7%, 2.7%, 5.2%, and 14.3% of participants randomised to placebo, SZC 5 g, 10 g, or 15 g once daily up to one month, respectively.	Oedema management as per investigator's medical judgment and standard clinical practice.
Hyperkalaemia (S-K $> 5.0$ mmol/L)	Lisinopril/valsartan can cause hyperkalaemia (especially in patients with impaired renal function) because they inhibit the release of aldosterone.  For participants randomised to placebo, there is risk of hyperkalaemia from lisinopril and valsartan.	Close monitoring of S-K after randomisation, including scheduled safety visits 2 and 7 days after randomisation.  Down-titration/withdrawal of lisinopril/valsartan if significant hyperkalaemia persists.  Rescue therapy available per standard of care/clinical practice.  SZC/placebo dosing based on local laboratory S-K and instructions in Section 6.6 and Appendix C .

S-Cr, serum creatinine; S-K, serum potassium; SZC, Sodium zirconium cyclosilicate.

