### **Events of Hypokalaemia and Oedema**

A tabulated overview of oedema-related AEs will be presented, with oedema-related AE defined through the following preferred terms: fluid overload, fluid retention, generalised oedema, hypervolaemia, localised oedema, oedema, oedema peripheral, peripheral swelling.

Instances of  $S-K < 3.5$  mmol/L at particular visits, as well as the number and percentage of participants with  $S-K < 3.5$  mmol/L at any point during a study phase, will be tabulated. Instances of  $S-K < 3.0$  and  $< 2.5$  mmol/L will be presented in a similar manner.

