| Section 4.2 Endpoint Analysis | 01 Dec 2022 | The list of covariates to be included in the models has been specified (consisting of treatment arm and the factors reflecting stratification). | Yes | For clarity and analysis optimization. |

| | | | | |
|--|----------------|---|-----|--|
| Section 4.2.1 Analysis of Primary Objective | 01 Dec 2022 | Choice of covariance structures (unstructured to independence) | Yes | Analysis optimization. |
| Section 4.2.1 Analysis of Primary Objective | 01 Dec 2022 | Addition of extra sensitivity analysis (two- slope SP model, repeated measures model with unstructured covariance structure, imputation of first post-ESKD eGFR value, tipping point analysis for lost to FU, replication of the main analysis using the original, age-corrected, eGFR formula) | Yes | As per discussion with the FDA, as well as a consequence of changing the eGFR formula (CSP v 2) and the change of covariance structure in the main analysis. |
| Section 4.2.1 Analysis of Primary Objective | 01 Dec 2022 | Addition of extra supplementary analysis (multiple post-ESKD eGFR values imputed) | Yes | As per discussion with the FDA, as well as ease of clinical interpretation. |
| Section 4.2.1 Analysis of Primary Objective | 01 Dec 2022 | Addition of extra subgroup analysis | Yes | As per discussion with the FDA, as well as ease of clinical interpretation. |
| Section 4.2.2 Analysis of the Secondary Objective 1 | 01 Dec 2022 | The derivation of the endpoint has been clarified | Yes | For clarity. |
| Section 4.2.7.3 Evaluation of potential impact of acute effects | 01 Dec 2022 | Further details regarding the supportive analysis of change in eGFR (pre vs post treatment) have been provided | Yes | For clarity. |
| Section 4.5.1 Safety analyses | 01 Dec 2022 | The presentation of rate of occurrence of AEs has been removed, replaced with a possibility to evaluate hazard ratios. | Yes | Optimization of the analysis in accordance to the recent guidance. |
| Section 6 References | 01 Dec 2022 | Addition of a reference | Yes | N/A |

| | | | | |
|--------------------|-------------|--|-----|--|
| Section 7 Appendix | 01 Dec 2022 | Creation of Appendix 7.1 The mapping of CKD aetiology class. A mapping of the CKD aetiology as collected in the eCRF to a different classification, used in analyses, has been added. | Yes | For programming purposes. |

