| Section 7 Appendix | 01 Dec 2022 | Creation of Appendix 7.2 The assignment of countries to regions. A mapping of countries to regions has been added. | Yes | For programming purposes. |
| Section 7 Appendix | 01 Dec 2022 | Creation of Appendix 7.2 Sample size calculation. | Yes | The sample size calculation present in CSP has been added to the SAP for readers convenience. |
| Section 3.3.1.2 | 22 Jan 2023 | Definition of phases updated | Yes | To accommodate some specific cases observed in the (blinded) data during dry run preparation. |
| Section 4.2 | 22 Jan 2024 | Deletion of a large part of supplementary and sensitivity analyses. | Yes | Due to the premature termination of the study, the decision was taken to slim down the scope of the CSR. All the main analyses remain as previously defined. However, majority of supportive and supplementary analyses have been removed as superfluous in view of the limited data availability. |
| Section 4.2 | 24 Apr 2024 | Simplification of the data exploration | Yes | For the same reason as above, even other simplifications have been introduced. For instance, no extensive exploration of missing data patterns will be performed. Some sub-group analyses have been removed. |
| Section 4.2.1.5 | 24 Apr 2024 | Minor change in sub-group analysis approach | Yes | The effect estimates will now be obtained for each sub-group separately, rather than from a global model via application of contrasts. Changed for simplicity of implementation. |

| | | | | |
|-------------|-------------|--|--|--|
| Section 4.2 | 24 Apr 2024 | Exclusion of the late measurements | No | Due to the termination of the study, the number of laboratory measurements later in the study is very limited. As such, all the lab-based analyses (majority of efficacy) will be performed on data obtained up to and including visit 17. |
| 4.2.6 | 24 Apr 2024 | Change of the repeated measurements analysis from mixed model to GEE | Yes | Relative ease of interpretation, as GEE works with marginal odds, rather than conditional ones, leading to a closer correspondence to a simple number (%) type of tabulation. |
| 4.5 | 24 Apr 2024 | Actual treatment removed from listings | Yes | |
| 4.5.1 | 24 Apr 2024 | All AEs resented by PT in decreasing frequency, rather than only the most common ones. Sorting now by SZC. | Yes | |
| 4.5.2 | 24 Apr 2024 | For all abnormality tabulations, only patients with normal values at baseline are included. | Yes | |

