2 CHANGES TO PROTOCOL PLANNED ANALYSES

No changes were made to the analyses as described in the CSP.

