4.5.1.2 Presentations

Adverse events (AE) will be summarised descriptively in accordance with the rules described in Section 3.3. Estimates of differences in AE profiles (e.g., hazard ratios, difference in probability of an event occurring within a pre-specified time interval) may also be presented, along with the corresponding CIs.

All AEs will be summarised by SOC and PT according to the latest MedDRA version available at the time of database lock.

Overall overview

An AE overview table will be created, with AEs falling within the following categories summarized by treatment group.

- Any AE
- Any SAE

- Any AE with outcome death
- Any AE leading to discontinuation of SZC or SZC/placebo
- Any AE leading to discontinuation of Lisinopril/valsartan
- Any AE leading to dose interruption of SZC or SZC/placebo
- Any AE leading to dose interruption of Lisinopril/valsartan
- Any AE leading to dose reduction of SZC or SZC/placebo
- Any AE leading to dose reduction Lisinopril/valsartan
- Any AE possibly related to SZC or SZC/placebo
- Any AE possibly related to Lisinopril/valsartan
- Any SAE possibly related to Lisinopril/valsartan
- Any SAE possibly related to SZC or SZC/Placebo

AEs, SAEs, DAEs and deaths, by system organ class and preferred term

A detailed overview of number, and percentage, of subjects with AEs, SAEs, DAEs and deaths in a particular SOC and PT class will be presented.

Most common AEs

A tabulation of the PT terms sorted by decreasing frequency (most common AEs in SZC arm on top) will be provided.

Intensity of AEs

An overview of the number and the percentage of subjects with AEs in a particular SOC, PT and intensity class (mild, moderate, severe) will be created. Subjects will be counted only once in each category. A subject with two AE in the same SOC and PT class of, e.g., both high and moderate intensity will be assigned the “high” intensity category, i.e., the more severe class.

Causality of AEs

Number and percentage of subjects with AEs considered as possibly related to each of the IPs (SZC/Placebo and Lisinopril/valsartan) will be tabulated by SOC and PT, in separate tabulations.

Events related to oedema, hypokalaemia, or hyperkalaemia

An overview of oedema-related AEs, with number and percentage of subjects with an event with a particular PT term, will be presented.

Number of subjects with AE classified as hypokalaemia, hyperkalaemia, or hyperkalaemia requiring rescue, will be tabulated in a similar manner.

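### The SAP's oedema definition drops one of the protocol's eight preferred terms, fluid overload, and nothing in the SAP declares it

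*SAP*

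**What the plan says.** Protocol Section 9.4.3, under the heading on hypokalaemia and oedema, promises a tabulated overview of oedema-related adverse events, with "oedema-related AE defined through the following preferred terms: fluid overload, fluid retention, generalised oedema, hypervolaemia, localised oedema, oedema, oedema peripheral, peripheral swelling". This is the protocol's analysis definition. The protocol uses the same set of terms descriptively in two other places: Section 2.2.2, on the identified adverse drug reactions of SZC, and Table 3, where the oedema risk "includes fluid overload, fluid retention, generalised oedema, hypervolaemia, localised oedema, oedema, oedema peripheral, peripheral swelling".

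SAP Section 4.5.1.1 gives its own definition: "Oedema-related events are defined as AEs with the following PT terms: Fluid retention, Generalised oedema, Hypervolemia, Localised oedema, Oedema, Oedema Peripheral, Peripheral swelling". Section 4.5.1.2 then plans the output that uses it: "An overview of oedema-related AEs, with number and percentage of subjects with an event with a particular PT term, will be presented". The same section also covers adverse events in general: "All AEs will be summarised by SOC and PT according to the latest MedDRA version available at the time of database lock".

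On departures from the protocol, SAP Section 2 states: "No changes were made to the analyses as described in the CSP".

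**The concern.** Both lists are closed. Neither has wording such as 'including' that would let a programmer add a term, so anyone building the table from the SAP would leave fluid overload out.

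The category affected is not incidental. Protocol Section 2.2.2 names two identified adverse drug reactions for SZC, oedema-related events and hypokalaemia, and each has its own planned presentation. Table 3 reports programme rates for the oedema category of 1.7% on placebo and 2.7%, 5.2% and 14.3% on SZC 5 g, 10 g and 15 g once daily, under a description that includes fluid overload. A seven-term overview from this trial would not be like-for-like with those figures, and a reader of the table would have no sign that a protocol-defined term was absent.

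**Working it through.** No power or sample-size figure is involved. The check compares the lists as sets, ignoring case and treating *Hypervolemia* and *hypervolaemia* as one term, and then looks for any declaration of a difference.

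**Step 1: the lists side by side.**

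| Preferred term | Protocol 9.4.3 | SAP 4.5.1.1 |
|---|---|---|
| Fluid overload | yes | **no** |
| Fluid retention | yes | yes |
| Generalised oedema | yes | yes |
| Hypervolaemia | yes | yes |
| Localised oedema | yes | yes |
| Oedema | yes | yes |
| Oedema peripheral | yes | yes |
| Peripheral swelling | yes | yes |
| **Total** | **8** | **7** |

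The protocol has 8 terms and the SAP has 7, and 8 − 7 = 1. The SAP contains no term that the protocol lacks. The lists in Protocol Section 2.2.2, Table 3 and Section 9.4.3 are identical as sets, so the protocol agrees with itself and the SAP is the only outlier.

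**Step 2: is the difference declared?**

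- SAP Section 2 says that nothing changed.
- The amendment history has two entries for Section 4.5.1. The one dated 01 Dec 2022 reads: "The presentation of rate of occurrence of AEs has been removed, replaced with a possibility to evaluate hazard ratios". The one dated 24 Apr 2024 concerns the preferred-term table, with terms now shown "in decreasing frequency, rather than only the most common ones. Sorting now by SZC".
- The 24 Apr 2024 entry for Section 4.5 concerns actual treatment in listings.
- The general entry of 29 May 2024 records only that text was revised.

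Entries that mention the oedema list: 0. The history has a column for agreement with the protocol and marks other items as not in line with it, for example the exclusion of late measurements and the removal of compliance. This item is not among them.

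**Step 3: what the omission does to counts.** Every SAP term is also a protocol term, so every participant who qualifies under the SAP also qualifies under the protocol. For a count of participants with at least one oedema-related event:

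N(SAP) = N(protocol) − n, with n ≥ 0,

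where n is the number of participants whose only qualifying event is coded fluid overload. The count can be too low, never too high.

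For the difference in proportions between arms, write a and b for the values of n in the SZC and placebo arms, and A and B for the arm sizes. The SAP definition shifts the difference by −(a/A − b/B). The documents give neither a nor b, so neither the size nor the sign of this shift can be stated.

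**The case against.** The mismatch itself is hard to dispute. The case on the other side concerns its consequence and how it arose.

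- **The undercount is conditional.** The SAP describes the overview as a tabulation by individual preferred term. Neither document commits to a row for participants with any oedema-related event. What is certain is one absent row. This stands, and the undercount is stated here only for the case where such a total is produced.
- **The information is not lost.** Events coded fluid overload would appear in the all-event tables by system organ class and preferred term, and in the frequency-sorted table. This also stands. However, those tables do not group the oedema terms, and grouping them is the purpose of a dedicated overview.
- **Coding version.** Adverse events are coded to the MedDRA version current at database lock, and the effect assumes that fluid overload is a separate preferred term in that version. The documents do not settle this, but they give no sign that it explains the omission. It limits certainty about the effect, not about the discrepancy.
- **Silence in the amendment history proves little.** The seven-term list may date from the initial SAP of 15 Dec 2021, in which case no revision entry would be expected. The statement in SAP Section 2 is also a blanket one that the SAP's own log contradicts on other items. A transcription slip is at least as plausible as a decision. All of this is fair, and no intent is inferred. The departure from the protocol is still undeclared.

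**Conclusion.** The discrepancy is real: the SAP definition covers 7 of the 8 protocol terms, omits only fluid overload, and does not say so. As written, the planned oedema overview is incomplete against the protocol's analysis definition by one row, and any participant-level total would be too low by n ≥ 0.

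The severity is minor. The other seven rows are unaffected, no primary or secondary hypothesis depends on the list, and the events remain visible elsewhere. The conclusion about the text rests on no assumption beyond reading the two spellings of hypervolaemia as the same term. Any effect on the output assumes that at least one event is coded to fluid overload as its own preferred term, which the documents do not show.

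**What to change.** Add fluid overload to the preferred-term list in SAP Section 4.5.1.1 and to the corresponding programming list, so that both match the eight terms of Protocol Section 9.4.3. If the omission is intended, record and justify it in the amendment history, marked as not in line with the protocol, and amend SAP Section 2 accordingly.

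The cost is one term in the SAP text and one in the programming list. No new data are needed.

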4.5.1.2 Presentations

Adverse events (AE) will be summarised descriptively in accordance with the rules described in Section 3.3. Estimates of differences in AE profiles (e.g., hazard ratios, difference in probability of an event occurring within a pre-specified time interval) may also be presented, along with the corresponding CIs.

All AEs will be summarised by SOC and PT according to the latest MedDRA version available at the time of database lock.

Overall overview

An AE overview table will be created, with AEs falling within the following categories summarized by treatment group.

- Any AE
- Any SAE

- Any AE with outcome death
- Any AE leading to discontinuation of SZC or SZC/placebo
- Any AE leading to discontinuation of Lisinopril/valsartan
- Any AE leading to dose interruption of SZC or SZC/placebo
- Any AE leading to dose interruption of Lisinopril/valsartan
- Any AE leading to dose reduction of SZC or SZC/placebo
- Any AE leading to dose reduction Lisinopril/valsartan
- Any AE possibly related to SZC or SZC/placebo
- Any AE possibly related to Lisinopril/valsartan
- Any SAE possibly related to Lisinopril/valsartan
- Any SAE possibly related to SZC or SZC/Placebo

AEs, SAEs, DAEs and deaths, by system organ class and preferred term

A detailed overview of number, and percentage, of subjects with AEs, SAEs, DAEs and deaths in a particular SOC and PT class will be presented.

Most common AEs

A tabulation of the PT terms sorted by decreasing frequency (most common AEs in SZC arm on top) will be provided.

Intensity of AEs

An overview of the number and the percentage of subjects with AEs in a particular SOC, PT and intensity class (mild, moderate, severe) will be created. Subjects will be counted only once in each category. A subject with two AE in the same SOC and PT class of, e.g., both high and moderate intensity will be assigned the “high” intensity category, i.e., the more severe class.

Causality of AEs

Number and percentage of subjects with AEs considered as possibly related to each of the IPs (SZC/Placebo and Lisinopril/valsartan) will be tabulated by SOC and PT, in separate tabulations.

Events related to oedema, hypokalaemia, or hyperkalaemia

An overview of oedema-related AEs, with number and percentage of subjects with an event with a particular PT term, will be presented.

Number of subjects with AE classified as hypokalaemia, hyperkalaemia, or hyperkalaemia requiring rescue, will be tabulated in a similar manner.

Key subject information tables

Key subject information will be provided for all SAEs, AEs with an outcome of death, and all AEs leading to IP discontinuation. This will include, e.g., the duration variables defined in the beginning of this section, outcome of an AE and action taken with respect to IP.

Listings

The listings provided may include, but may not be limited to:

- All AE
- All AE of hypokalemia.
- SAE for subjects who were enrolled but did not enter initiation phase.

All listings will be created for during the study time period, and will include, among others, planned treatment arm and planned dose of both of the IPs.

